2.1.7 Phase II Dose Expansion

A Simon two-stage design will be used. Based on the primary endpoint of objective response rate, twenty evaluable subjects will be enrolled in Stage I portion of Phase II. If there are at least 2 responses among the 20 evaluable subjects, an additional 18 evaluable subjects will be entered. If there are fewer than 2 responses among the first twenty evaluable subjects, then this trial will be stopped early for futility. If at least 12 are observed among the 38 evaluable subjects, then the treatment will be considered effective.

Subjects from the Phase I part of the study who are treated at the RP2D may be included in the efficacy assessments in Stage I of the Phase II part of the study.

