8.2.3 Analysis of Anti-Tumor Activity

Descriptive statistics will be used to summarize all demographic and analytic data. Continuous data will be summarized using means, standard deviation, range, etc. Categorical data will be summarized using frequency tables.

Tumor response analyses will be based on definitions of responses according to both RECIST v1.1 and immune-related response criteria (irRECIST).

Objective response is defined as a complete or partial response, as determined by investigator assessment using RECIST and irRECIST. Subjects with missing or no response assessments will be classified as non-responders. For the primary objective, a one-sided exact binomial test will be used to assess whether the ORR is significantly greater than 20% in subjects taking a combination of pembrolizumab and cabozantinib.

Clinical benefit rate (CR + PR +SD) and duration will also be recorded.

Among subjects with an objective response, duration of response will be defined as the time from first occurrence of a documented objective response until the time of documented disease progression or death from any cause during the study, whichever occurs first. For all other subjects, duration of objective response will be censored at the day of the last tumor assessment.

Progression-free survival (PFS) will be defined as the time from study treatment initiation (Cycle 1, Day 1) to the first occurrence of documented disease progression or death from any cause during the study, whichever occurs first. For subjects who do not have documented progressive disease or death during the study, PFS will be censored at the day of the last tumor assessment.

Overall survival (OS) will be defined as the time from study treatment initiation (Cycle 1, Day 1) to death from any cause. For subjects who do not have documented death during or after the study, OS will be censored at the day of known survival status.

In subjects with bone metastases, time to progression of bone metastases or skeletal related event (SRE, defined as pathologic fracture, spinal cord compression, and radiation to bone or surgery to bone related to cancer) will also be recorded from Cycle 1 Day 1 to the time of progression or SRE.

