8.2.5 Sample Size

The proposed study is a single-arm, phase I/II study of pembrolizumab in combination with cabozantinib in subjects with metastatic RCC. We will use a Simon two-stage design for the phase II portion this study based on the primary endpoint of objective response rate. The planned enrollment for this study is approximately 25-55 total subjects, to account for screen failures, in order to achieve 6-9 evaluable subjects in Phase I dose escalation and 20-38 evaluable subjects in Phase II dose expansion. Subjects from the Phase I part of the study who are treated at the RP2D may be included in the efficacy assessments in Stage I of the Phase II part of the study.

Phase I:

Any subject who does not complete the DLT assessment window for any reason other than a DLT will be considered non-evaluable for dose-escalation decisions and MTD and RP2D assessment and will be replaced by an additional subject at that same dose level.

Table 12 describes the probability of not observing any DLTs in 3 subjects, and the probability of observing fewer than two DLTs in 6 subjects for different underlying DLT rates.

| Underlying DLT Rate | Probability of Observing No DLTs in 3 Subjects | Probability of Observing Fewer Than Two DLTs in 6 Subjects |
|---------------------|---|---|
| 0.10 | 0.73 | 0.89 |
| 0.20 | 0.51 | 0.66 |
| 0.33 | 0.30 | 0.36 |
| 0.40 | 0.22 | 0.23 |
| 0.50 | 0.13 | 0.11 |
| 0.60 | 0.06 | 0.04 |

Table 12: Probability of Observing DLTs for Different Underlying DLT Rates

For a given adverse event with a true rate of 10%, 5%, or 1%, the probability of observing at least one such adverse event in a given cohort of 6 subjects is 47%, 26.5%, and 5.8%, respectively.

Phase II:

The Simon's two-stage design will be implemented to test the null hypothesis that $ORR \le 0.20$ versus the alternative that $ORR \ge 0.50$. After the enrollment of 20 evaluable patients in the first stage, the trial will be terminated if 2 or fewer respond. If the trial goes on to the second stage, a total of 38 patients will be studied. If the total number responding is greater than 12, the treatment is considered effective.

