This two-stage design has an expected sample size of 34.29 and a probability of early termination of 0.206. If the drug is actually not effective, there is a 0.029 (satisfied the 0.05 type I error rate constraint) probability of concluding that it is. If the drug is actually effective, there is a 0.017 probability of concluding that it is not, which corresponding to a 98% power (satisfied the 90% power constraint).

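### Sections 2.1.7 and 8.2.5 give different Simon two-stage cut-offs, and the Section 2.1.7 version has a type I error of 6.2% against the plan's 5% limit

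*Combined protocol and SAP*

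**What the plan says.** Section 2.1.7 (Phase II Dose Expansion) enters 18 more subjects once 2 of the first 20 have responded. Its futility rule is "If there are fewer than 2 responses among the first twenty evaluable subjects, then this trial will be stopped early for futility", and its efficacy rule is "If at least 12 are observed among the 38 evaluable subjects, then the treatment will be considered effective".

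Section 8.2.5 (Sample Size, Phase II) uses the same stage sizes with other cut-offs. On futility, "After the enrollment of 20 evaluable patients in the first stage, the trial will be terminated if 2 or fewer respond". On efficacy, "If the total number responding is greater than 12, the treatment is considered effective", which means 13 or more of 38.

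Section 8.2.5 then describes the design's performance: "This two-stage design has an expected sample size of 34.29 and a probability of early termination of 0.206". It also gives a type I error of 0.029 against a 0.05 constraint, and a type II error of 0.017 (98% power) against a 90% power constraint. The null is an ORR of at most 0.20 and the alternative an ORR of at least 0.50.

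For the primary analysis, Section 8.2.3 specifies a one-sided exact binomial test of the response rate against 20%.

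**The concern.** These are two different rules, not two wordings of one rule. With exactly 2 responses in 20, Section 2.1.7 continues to a further 18 subjects and Section 8.2.5 stops the trial. With exactly 12 responses in 38, Section 2.1.7 calls the treatment effective and Section 8.2.5 does not. No other text reconciles the two or says which section governs.

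Only one set of operating characteristics is printed, so at most one rule can have them. If the site works from Section 2.1.7, which is the operational description of Phase II, it may be running a test that misses the plan's own type I error limit. The trial is open-label and response is assessed by the investigator, so two efficacy thresholds also leave room to choose between them once the count is known.

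**Working it through.** **Inputs.** Stage 1 size 20, total 38, hence 18 in stage 2 (both sections). Null rate 0.20, alternative 0.50, type I error limit 0.05 (Section 8.2.5). Write r1 for the largest stage 1 count that stops the trial and r for the largest final count that is not called effective. Section 8.2.5 is r1 = 2, r = 12. Section 2.1.7 is r1 = 1, r = 11.

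**Formulas.**
- Probability of early termination: PET = P(Bin(20, p) ≤ r1).
- Expected sample size: EN = 20 + 18 × (1 − PET).
- Probability of declaring efficacy: the sum over x > r1 of P(Bin(20, p) = x) × P(Bin(18, p) ≥ r + 1 − x). This is the type I error at p = 0.20 and the power at p = 0.50.

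**Stage 1 under the null, p = 0.20.**
- P(0) = 0.8^20 = 0.0115
- P(1) = 20 × 0.2 × 0.8^19 = 0.0576
- P(2) = 190 × 0.2² × 0.8^18 = 0.1369

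**Reproducing the plan's figures with the Section 8.2.5 rule.** PET = 0.0115 + 0.0576 + 0.1369 = 0.206 (0.2061 unrounded). EN = 20 + 18 × 0.7939 = 34.29. Type I error = 0.0288. Type II error = 0.0168. All four printed values are recovered to the precision given.

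**The Section 2.1.7 rule.** PET = 0.0115 + 0.0576 = 0.069 (0.0692 unrounded). EN = 20 + 18 × 0.9308 = 36.75. Type I error = 0.0623. Power at 0.50 = 0.9931. None of the printed values is recovered.

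**Which cut-off does the damage.** All four pairings:

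| Stop at or below (of 20) | Effective at or above (of 38) | PET at 0.20 | EN at 0.20 | Type I error | Power at 0.50 |
|---|---|---|---|---|---|
| 2 (8.2.5) | 13 (8.2.5) | 0.2061 | 34.29 | 0.0288 | 0.9832 |
| 1 (2.1.7) | 12 (2.1.7) | 0.0692 | 36.75 | 0.0623 | 0.9931 |
| 2 | 12 | 0.2061 | 34.29 | 0.0622 | 0.9930 |
| 1 | 13 | 0.0692 | 36.75 | 0.0288 | 0.9832 |

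Moving the final cut-off from 13 to 12 takes the type I error past 0.05 whichever stage 1 rule is used. Moving the stage 1 cut-off leaves the type I error almost unchanged and alters only early stopping and expected sample size.

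**Against the Section 8.2.3 test.** Ignoring the interim stop, P(Bin(38, 0.20) ≥ 12) = 0.0623 and P(Bin(38, 0.20) ≥ 13) = 0.0288. At 12/38 the exact one-sided p-value is therefore 0.062, and at 13/38 it is 0.029.

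**How often the two rules would part.**

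| True ORR | Probability of exactly 2/20 | Probability of exactly 12/38 |
|---|---|---|
| 0.20 | 0.137 | 0.034 |
| 0.30 | not calculated | 0.135 |
| 0.50 | 0.0002 | 0.0098 |

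**The case against.** Sections 8.2.5 and 8.2.3 sit in the statistical chapter, and Section 8.2.5 is complete and internally consistent. A statistician can see which rule was designed, and the arithmetic printed there is correct. That lowers the practical risk. It does not remove it, because nothing ranks one section over the other.

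The consequences are also limited in some respects, and these points stand:

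- Only the final cut-off breaches the limit, by 1.2 percentage points (0.062 against 0.05). The stage 1 difference is a matter of early stopping.
- Power meets the 90% constraint under both rules. If the true response rate is 50%, the chance of landing on either disputed count is below 1%. The conflict matters mainly if the combination is weak or intermediate.
- Section 8.2.3 names no significance level. Saying that its test would not reject at 12/38 relies on carrying over the 0.05 from Section 8.2.5. That p-value also ignores the interim look, though the numerical difference is negligible.

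Timing needs care as well. The document is dated 6/17/2021, and Section 5.2.1.3.2 provides for patients already past 35 cycles at the 20-OCT-2020 version. The stage 1 decision may already have been made; the documents do not say. An unexplained edit now could look like a boundary chosen after seeing data.

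None of this reconciles the two sections.

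**Conclusion.** The concern holds. The primary decision rule contradicts itself at 2/20 and at 12/38, and the Section 2.1.7 version has an exact one-sided type I error of 0.062, more than double the 0.029 attained by the designed rule. It also lowers the null probability of early stopping to about a third (0.069 against 0.206) and raises the null expected sample size by about 2.5 subjects (36.75 against 34.29).

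Of the four pairings of the documents' cut-offs, only the Section 8.2.5 pair reproduces all the stated operating characteristics, so that is the rule the plan was built on. The calculation assumes independent binomial responses, exactly 20 and 38 evaluable subjects, and futility stopping that is followed as written. It must be fixed because it decides the primary endpoint.

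**What to change.** Amend the three boundary sentences in Section 2.1.7 to agree with Section 8.2.5: stop if 2 or fewer of the first 20 evaluable subjects respond, continue if 3 or more respond, and declare the treatment effective only if 13 or more of 38 respond. Check the trial diagram in Section 2.2, which could not be seen, for the same cut-offs.

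In the amendment rationale, state that Section 8.2.5 governs because the printed operating characteristics were computed from it. If the stage 1 analysis has been done, record its date, the response count and the rule applied. Even if the trial continued under the Section 2.1.7 stage 1 rule, keeping 13/38 as the final cut-off holds the type I error at 0.0288.

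The cost is a short text amendment with the IRB approval that Section 10.7 requires. Sample size, hypotheses and procedures do not change.

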2.1.8 Archival Tumor and Optional Fresh Tissue Biopsies

Archival tumor tissue is mandatory for enrollment in both the Phase I dose escalation and Phase II dose expansion parts of the study.

In addition, subjects may consent for optional fresh tissue biopsies at baseline (during screening period) and/or post-treatment at approximately 3-6 weeks (during cycle 2) after initiation of study treatment.

2.2 Trial Diagram

3.0 OBJECTIVES

3.1 Primary Objectives

The primary objective for this study is to determine the efficacy based on objective response rate [ORR = complete response (CR) + partial response (PR)] of pembrolizumab and cabozantinib when administered in combination in subjects with locally advanced or metastatic renal cell carcinoma.

3.2 Secondary Objectives

The secondary objectives for this study are:

- To characterize dose-limiting toxicities (DLTs), maximum tolerated dose (MTD), and recommended phase 2 dose (RP2D) for the combination.
- To assess other measures of anti-tumor activity of the combination of pembrolizumab and cabozantinib in subjects with locally advanced or metastatic renal cell carcinoma.
 - irRECIST (Immune-related response criteria) response
 - Progression-free survival
 - Overall survival
 - Time to progression of overall disease
 - Time to progression of bone metastasis or skeletal-related event
 - Clinical benefit rate [complete response (CR) + partial response (PR) + stable disease (SD)]
 - Duration of response or disease stability
 - Duration on treatment in subjects treated beyond progression

3.3 Exploratory Objectives

The exploratory objectives for this study may include:

ο Bone turnover markers, such as β C-terminal telopeptide (β -CTX), bone specific alkaline phosphatase, and procollagen type 1 amino-terminal propeptide (P1NP).

- Bone scan responses
- PD-L1 IHC testing on archival samples.
- PD-L1 IHC testing on fresh tumor baseline and/or post-treatment samples.
- o Evaluation of immuno-oncology markers

4.0 BACKGROUND & RATIONALE

4.1 Background

Over the past decade, multiple vascular endothelial growth factor (VEGF) and molecular target of rapamycin (mTOR) pathway targeted therapies have been approved and have significantly improved the morbidity and mortality among subjects with advanced or metastatic renal cell carcinoma (mRCC). Nevertheless, mRCC remains a largely incurable disease. Tyrosine kinase inhibitors (TKI) and VEGF-directed antibodies are widely used as standard first- and second-line treatments for metastatic RCC. Despite the improvements seen with the currently available VEGF-directed therapies, treatment resistance and disease progression occur in the majority of subjects with continued treatment and these agents do not produce durable responses.[1] Acquired resistance to vascular endothelial growth factor (VEGF) pathway inhibitors is frequently mediated through the activation of alternative signaling pathways that restore tumor perfusion, including upregulation of the expression of angiopoietins, c-MET, activin receptor-like kinase-1 (ALK-1) receptor and interleukin 8 (IL-8), and loss of p53 function.[2] In addition, VEGF also acts as an immunosuppressive molecule and can inhibit maturation of dendritic cells, promote immune suppressive cell infiltration and enhance immune checkpoint molecules expression.[3]

Renal cell carcinoma is an immunogenic tumor with a dysfunction immune cell infiltrate that allows malignant progression through evasion of immune surveillance. Novel immunemodulating agents that target cytotoxic T-lymphocyte-associated antigen 4 (CTLA-4) and programmed death receptor-1 (PD-1) significantly enhances antitumor immunity.[4] The benefit of anti-PD-1 antibodies in the treatment of mRCC was confirmed in the CheckMate 025 study, which was a phase III study of nivolumab (an anti-PD-1 antibody) vs. everolimus in the second-line treatment of mRCC. Compared to everolimus, nivolumab showed significant improvements in overall survival (25.0 vs. 19.6 months; HR 0.73; P=0.002) and objective response rate (25% vs. 5%).[5]

Recent major discoveries in tumor immunology and agents that can trigger immune responses, along with better understanding of the mechanisms of VEGF inhibitor therapy provide rationale for combination therapies in the treatment of mRCC. There are multiple proposed mechanisms of synergy between inhibiting both VEGF- and PD-1. In addition to angiogenic

activity, VEGF may promote immunosuppression by inhibiting dendritic cell maturation and VEGF inhibitors reverse this immunosuppression by reducing numbers of circulating regulatory T cells and myeloid-derived suppressor cells and allowing for better maturation of dendritic cells.[1, 6, 7] VEGF inhibitors such as sunitinib may also enhance CD4+ T and CD8+ T cell intratumoral infiltration.[8] In mouse models, VEGF-A has been shown to modulate the expression of inhibitory checkpoints such as PD-1 on CD8+ T cell in tumors.[9] These data provide rationale for clinical investigations of combined angiogenesis inhibition and immunotherapy/immune checkpoint inhibition.

4.1.1 Pharmaceutical and Therapeutic Background

4.1.1.1 PD-1/PD-L1 Blockade

The importance of intact immune surveillance in controlling outgrowth of neoplastic transformation has been known for decades. Accumulating evidence shows a correlation between tumor-infiltrating lymphocytes (TILs) in cancer tissue and favorable prognosis in various malignancies. In particular, the presence of CD8+ T-cells and the ratio of CD8+ effector T-cells / FoxP3+ regulatory T-cells seems to correlate with improved prognosis and long-term survival in many solid tumors.

The PD-1 receptor-ligand interaction is a major pathway hijacked by tumors to suppress immune control. The normal function of PD-1, expressed on the cell surface of activated Tcells under healthy conditions, is to down-modulate unwanted or excessive immune responses, including autoimmune reactions. PD-1 (encoded by the gene Pdcd1) is an Ig superfamily member related to CD28 and CTLA-4 which has been shown to negatively regulate antigen receptor signaling upon engagement of its ligands (PD-L1 and/or PD-L2). The structure of murine PD-1 has been resolved. PD-1 and family members are type I transmembrane glycoproteins containing an Ig Variable-type (V-type) domain responsible for ligand binding and a cytoplasmic tail which is responsible for the binding of signaling molecules. The cytoplasmic tail of PD-1 contains 2 tyrosine-based signaling motifs, an immunoreceptor tyrosine-based inhibition motif (ITIM) and an immunoreceptor tyrosine-based switch motif (ITSM). Following T-cell stimulation, PD-1 recruits the tyrosine phosphatases SHP-1 and SHP-2 to the ITSM motif within its cytoplasmic tail, leading to the dephosphorylation of effector molecules such as CD3ζ, PKCθ and ZAP70 which are involved in the CD3 T-cell signaling cascade. The mechanism by which PD-1 down modulates T-cell responses is similar to, but distinct from that of CTLA-4 as both molecules regulate an overlapping set of signaling proteins. PD-1 was expressed on activated lymphocytes including peripheral CD4+ and CD8+ T-cells, B-cells, T regs and Natural Killer cells. Expression has also been shown during thymic development on CD4-CD8- (double negative) T-cells as well as subsets of macrophages and dendritic cells. The ligands for PD-1 (PD-L1 and PD-L2) are constitutively expressed or can be induced in a variety of cell types, including non-hematopoietic tissues as well as in various tumors. Both ligands are type I transmembrane receptors containing

both IgV- and IgC-like domains in the extracellular region and contain short cytoplasmic regions with no known signaling motifs. Binding of either PD-1 ligand to PD-1 inhibits T-cell activation triggered through the T-cell receptor. PD-L1 is expressed at low levels on various non-hematopoietic tissues, most notably on vascular endothelium, whereas PD-L2 protein is only detectably expressed on antigen-presenting cells found in lymphoid tissue or chronic inflammatory environments. PD-L2 is thought to control immune T-cell activation in lymphoid organs, whereas PD-L1 serves to dampen unwarranted T-cell function in peripheral tissues. Although healthy organs express little (if any) PD-L1, a variety of cancers were demonstrated to express abundant levels of this T-cell inhibitor. PD-1 has been suggested to regulate tumor-specific T-cell expansion in subjects with melanoma (MEL). This suggests that the PD-1/PD-L1 pathway plays a critical role in tumor immune evasion and should be considered as an attractive target for therapeutic intervention.

Pembrolizumab is a potent and highly selective humanized monoclonal antibody (mAb) of the IgG4/kappa isotype designed to directly block the interaction between PD-1 and its ligands, PD-L1 and PD-L2. KeytrudaTM (pembrolizumab) is currently approved in the United States for the treatment of melanoma, non-small cell lung cancer, small cell lung cancer, , head and neck squamous cell carcinoma, classical Hodgkin Lymphoma, primary mediastinal large B-cell lymphoma, ulcerative colitis, microsatellite instability-high tumors, gastric or gastroesophageal junction adenocarcinoma, esophageal cancer, cervical cancer, hepatocellular carcinoma, Merkel cell carcinoma, RCC, endometrial carcinoma, tumor mutational burden – high cancer, cutaneous Squamous Cell Carcinoma, Microsatellite instability-high cancer or mismatch repair deficient Colorectal Cancer.

4.1.1.2 MET and VEGFR2 in Renal Cell Carcinoma

Hepatocyte growth factor receptor protein (MET) and the VEGF receptor 2 (VEGFR2) are receptor tyrosine kinases that play a role in the promotion of tumor cell growth, invasiveness, metastasis, and/or angiogenesis in multiple tumor types including RCC.[10] Clear cell renal carcinomas commonly arise due to mutations in the tumor suppressor von Hippel-Lindau (VHL) gene which trigger an accumulation of hypoxia inducing factor (HIF) protein, which leads to an increase in expression of VEGF and of the receptor tyrosine kinase MET, resulting in angiogenesis, tumor cell proliferation, and invasive growth.[11] High MET expression has been observed in bone and brain metastases in subjects with mRCC and is associated with poor pathologic features and poor prognosis in RCC.[12-14]

Cabozantinib is an oral, small molecule tyrosine kinase inhibitor that targets MET, VEGFR2/KDR, RET, KIT, FLT3, and AXL. In a phase III clinical trial comparing cabozantinib vs. everolimus in subjects with mRCC who have progressed after a VEGFR-targeted therapy, cabozantinib demonstrated improved median progression-free survival (7.4 vs. 3.8 months), objective response rate (21% vs. 5%), and overall survival (HR 0.67, P<0.005).[15] In the phase II CABOSUN study comparing cabozantinib versus sunitinib in the

first-line setting for patients with intermediate- and poor-risk mRCC, cabozantinib was associated with statistically increased median progression-free survival (8.2 months vs 5.6 months), lower rate of progression or death (HR 0.66), and improved overall response rate (46% vs 18%) compared to sunitinib. [16] Based on these two studies, cabozantinib is currently approved for first-line, as well as, second-/subsequent-line treatment for metastatic renal cell carcinoma.

